## **9.3 Safety Assessments**

The safety, reactogenicity, and tolerability of a 2-dose schedule of CVnCoV will be assessed as described below.

### **9.3.1 Safety Assessments Specific for Subjects in the Immunogenicity/Reactogenicity Subset**

- Reactogenicity will be assessed daily on each vaccination day and the following 7 days by collection of solicited local AEs (injection site pain, redness, swelling, and itching) and systemic AEs (fever, headache, fatigue, chills, myalgia, arthralgia, nausea/vomiting, and diarrhea) using eDiaries. In addition, other indicators of safety will be collected (e.g., body temperature).
- The eDiary will also be used as a memory aid for the subject for the collection of unsolicited AEs on each vaccination day and the following 28 days.

### **9.3.2 Safety Assessments for All Subjects**

- Medically-attended AEs will be collected through 6 months after the second trial vaccination.
- AESIs will be collected through 1 year after the second trial vaccination. AESIs to be monitored include pIMDs, AESIs for SARS-CoV-2 vaccines, and non-serious intercurrent medical conditions that may affect the immune response to vaccination (Appendix 9).
- SAEs will be collected through 1 year after the second trial vaccination.
- AEs leading to vaccine withdrawal or trial discontinuation will be collected through 1 year after the second trial vaccination.

{If the subject does not receive their second trial vaccination, the AE follow-up time (6 months or 1 year) will be determined based on the date scheduled for their second vaccination on Day 29}.

- The eDiary will be used as a memory aid for the subject for the collection of medically-attended AEs, AESIs, and SAEs.

### **9.3.3 Adverse Events**

Definitions of AEs/SAEs, procedures for recording, evaluating, follow-up and reporting of AEs/SAEs/pregnancy/overdose, as well as assessments of intensity and causality of AEs, are provided in Appendix 10.

It is important to note that COVID-19 illness and its complications/sequelae are consistent with the efficacy endpoints of the trial and, as such, should not be recorded as AEs. These data will be captured on the relevant eCRF pages for cases of COVID-19 illness that occur in the trial, which are expected outcomes of the trial. Therefore, COVID-19 illness and its complications/sequelae will not be reported according to the standard expedited process for SAEs, even though the event may meet the criteria for an SAE. COVID-19 is to be reported as an AESI, according to Appendix 9.

#### **9.3.3.1 Solicited Adverse Events**

An eDiary will be distributed to all subjects in the Immunogenicity/Reactogenicity Subset for collection of solicited local AEs (injection-site pain, redness, swelling and itching) and solicited systemic AEs (fever, headache, fatigue, chills, myalgia, arthralgia,

nausea/vomiting and diarrhea) on the day of vaccination and the following 7 days. Subjects will be given a thermometer to measure body temperature orally and a measuring tape to determine the size of local injection-site reactions. Subjects will be instructed on how to enter the solicited AEs daily for 7 days in the eDiary.

Solicited AEs will be assessed on an intensity scale (Table 3 and Table 4). By definition, all local solicited AEs are considered related to trial vaccination. For solicited systemic AEs, the Investigator will assess the relationship between trial vaccine and occurrence of each AE and make an assessment of intensity for each AE.

If concerning to the subject or of prolonged duration, solicited Grade 3 AEs should be reported to the Investigator immediately. In case of related Grade 3 solicited AEs reported for more than 1 day on the eDiary, the subject will be questioned to establish the total duration of the AE as exactly as possible.

**Table 3 Intensity Grading\* for Solicited Local Adverse Events**

AE	Grade	Definition
Pain at Injection Site	0	Absent
	1	Does not interfere with activity
	2	Interferes with activity and/or repeated use of non-narcotic pain reliever > 24 hours
	3	Prevents daily activity and/or repeated use of narcotic pain reliever
Redness	0	< 2.5 cm
	1	2.5 – 5 cm
	2	5.1 – 10 cm
	3	> 10 cm
Swelling	0	< 2.5 cm
	1	2.5 – 5 cm and does not interfere with activity
	2	5.1 – 10 cm or interferes with activity
	3	> 10 cm or prevents daily activity
Itching	0	Absent
	1	Mild, no interference with normal activity
	2	Moderate, some interference with normal activity
	3	Significant, prevents normal activity

\*FDA toxicity grading scale [34].

**Table 4 Intensity Grading\* for Solicited Systemic Adverse Events**

Adverse Event	Grade	Definition
Fever	0	< 38°C
	1	≥ 38.0 – 38.4°C
	2	≥ 38.5 – 38.9°C
	3	≥ 39°C
Headache	0	Absent
	1	Mild, no interference with normal activity
	2	Moderate, some interference with normal activity and/or repeated use of non-narcotic pain reliever > 24 hours
	3	Significant; any use of narcotic pain reliever and/or prevents daily activity
Fatigue	0	Absent
	1	Mild, no interference with normal activity
	2	Moderate, some interference with normal activity
	3	Significant, prevents normal activity
Chills	0	Absent
	1	Mild, no interference with normal activity
	2	Moderate, some interference with normal activity
	3	Significant, prevents normal activity
Myalgia	0	Absent
	1	Mild, no interference with normal activity
	2	Moderate, some interference with normal activity
	3	Significant, prevents normal activity
Arthralgia	0	Absent
	1	Mild, no interference with normal activity
	2	Moderate, some interference with normal activity
	3	Significant, prevents normal activity
Nausea/ Vomiting	0	Absent
	1	Mild, no interference with activity and/or 1 – 2 episodes/ 24 hours
	2	Moderate, some interference with activity and/or >2 episodes/ 24 hours
	3	Significant, prevents daily activity, requires outpatient IV hydration
Diarrhea	0	Absent
	1	2 – 3 loose stools over 24 hours
	2	4 – 5 stools over 24 hours
	3	6 or more watery stools over 24 hours or requires outpatient IV hydration

\*FDA toxicity grading scale [34]; IV = Intravenous.

### 9.3.3.2 Unsolicited Adverse Events and Serious Adverse Events

Unsolicited AEs occurring on the day of vaccination and the following 28 days will be recorded by subjects included in the Immunogenicity/Reactogenicity Subset for each of the 2 trial vaccinations.

For all subjects, medically-attended AEs will be collected through 6 months after the second trial vaccination. AESIs will be collected through 1 year after the second trial vaccination (see Section 9.3.3.3). SAEs will be collected through 1 year after the second trial vaccination.

Medically-attended AEs are defined as AEs with medically-attended visits that are not routine visits for physical examination or vaccination, such as visits for hospitalization, an emergency room visit, or an otherwise unscheduled visit to or from medical personnel (medical doctor) for any reason.

The occurrence of AEs (serious and non-serious) will be assessed by non-directive questioning of the subject at each visit. AEs volunteered by the subject during or between visits as eDiary entries or detected through observation, physical examination, laboratory test, or other assessments during the entire trial, will be recorded in the eCRF if they fulfil the definitions as specified in section 9.3.2. Subjects should be instructed to report immediately any AEs with serious symptoms, subjective complaints or objective changes in their well-being to the Investigator or the site personnel, regardless of the perceived relationship between the event and the trial vaccine.

The Investigator will assess the relationship between trial vaccine and occurrence of each AE/SAE.

Non-serious intercurrent medical conditions that may affect the immune response to vaccination will also be collected throughout the trial.

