### 4.2 Endpoints

#### 4.2.1 Primary Endpoints

##### Primary Safety Endpoints

- Occurrence, intensity and relationship of medically-attended AEs collected through 6 months after the second trial vaccination in all subjects.
- Occurrence, intensity and relationship of SAEs and AESIs collected through 1 year after the second trial vaccination in all subjects.
- Occurrence of fatal SAEs through 1 year after the second trial vaccination in all subjects.
- Occurrence of AEs leading to vaccine withdrawal or trial discontinuation through 1 year after the second trial vaccination in all subjects.
- Occurrence, intensity and duration of each solicited local AE within 7 days after each trial vaccination in a subset of subjects.
- Occurrence, intensity, duration of each solicited systemic AE within 7 days after each trial vaccination in a subset of subjects.
- Occurrence, intensity and relationship of unsolicited AEs occurring within 28 days after each trial vaccination in a subset of subjects.

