## 10 STATISTICAL CONSIDERATIONS

### 10.1 Sample Size Determination

#### 10.1.1 Primary Safety Objective

While solicited vaccine reactions are expected, AEs that would limit product development may arise. Table 5 below indicates the probability of observing at least 1 AE in the trial when the true incidence of the AE with CVnCoV is 1:1000, 5:1000 or 1:100.

With a total of 1,680 subjects receiving CVnCoV (840 for each lot), AEs with a true incidence of 1:1000 will likely be observed in this trial with a 81.4% probability of observing at least one. Additionally, observation of 0 AE in 1,680 subjects would be associated with a 95% confidence that the true incidence rate of this AE is below 1.8:1000.

With a total of 840 subjects included in the Immunogenicity/Reactogenicity subset and receiving CVnCoV (420 for each lot), solicited/unsolicited AEs with a true incidence of 5:1000 will likely be observed in this trial with a 98.5% probability of observing at least one. Observation of 0 AE in 840 subjects would be associated with a 95% confidence that the true incidence rate of this AE is below 3.6:1000.

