## Reporting of AEs

### AE Reporting

It is the responsibility of the Investigator to document all AEs that occur during the trial in the source documents. AEs will be elicited by asking the subject a non-leading question, for example, 'Have you experienced any new or changed symptoms since we last asked/since your last visit?'.  
The Investigator must document all AEs that occur during the observation period set in this protocol and which fulfil the conditions as outlined in section 9.3.2. Safety Assessments for All Subjects on the screens provided in the eCRF.

The following approach will be taken for documentation:

The following approach will be taken for documentation:

**All Adverse Events** (whether serious or non-serious) which need to be reported according to section 9.3.2. must be documented on the "Adverse Event" screen of the eCRF. All AEs will be described using the sign, symptom, or medical diagnosis on the AE eCRF in standard medical terminology in order to avoid the use of vague, ambiguous, or colloquial expressions. Each AE will be defined as serious or non-serious according to the definitions in the section above. The Investigator will evaluate the severity of each AE and causal relationship of the event to the trial vaccine.

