**Protocol Version 5.0: 22 December 2021**

Section # and Name	Description of Important Change	Brief Rationale
Protocol Approval Signatures	New Medical Responsible Person [REDACTED]	Change of responsibility
SAE Hotline and Medical Monitor Contact	Added e-mail address for post-trial safety reporting	Change of safety reporting e-mail address after end of trial
Synopsis	Trial will remain blinded until approval of study protocol version 3.0.	Clarification

Synopsis / Schedule of Trial Assessments Table 1, 2 and 3
 
3.1.4 Trial Rationale
 
4.1.2 Secondary Endpoints
 
4.2 Endpoints
 
4.3 Estimands
 
5.1 Overall Design
 
5.2 Scientific Rationale for Trial Design
 
9.1.1.10; 9.1.2.7 End of Trial Visit
 
9.2.1.1.1 Routine Surveillance for COVID-19
 
9.4 Immunogenicity Assessments
 
10 Statistical Considerations
	
Assessment of cell mediated immune (CMI) response cancelled.
 
Comparison of efficacy by pooling of results with study COVID19-5-P-002 cancelled.
 
Limitation of immunogenicity analyses to 100 CVnCoV subjects per lot and 50 placebo subjects and to the following time points: Baseline, Day 29 and Day 43.
 
Assessment of seroconversion to the N-protein of SARS-CoV-2 at Day 393 cancelled.
 
Assessment of efficacy of CVnCoV in the prevention or reduction of asymptomatic infections cancelled.
	
Analyses no longer required.

	
Measurement of antibody responses for all Covid-19 cases that occur in the trial cancelled.
 
For positive RT-PCR tests, viral RNA of the SARS-CoV-2 sequencing to identify S protein variants no longer required.
	

1. Synopsis
 
5.1 Overall Design
 
9.2.1.3 COVID-19 Case Definition for the Efficacy Analysis
 
9.2.1.4 Adjudication of COVID-19 Cases
 
9.3.8.2 Adjudication Committee
	
Efficacy cases must no longer be confirmed by adjudication
	
Confirmation no longer required

9.3.3.2 Safety Assessments for All Subjects
 
Appendix 12 Adverse Events: Definitions and Procedures for Recording, Evaluating, Follow-up, and Reporting
	
AE recording only to be done for criteria defined in section 9.3.2
	
Clarification

8 Discontinuation / Withdrawal Criteria
	
Withdrawal procedure for placebo subjects added
	
Clarification

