10.5 AEs

An AE is any untoward medical occurrence in a subject which does not necessarily have to have a causal relationship with the investigational product. In this trial, confirmed cases of COVID-19 and complications/sequelae are not considered as AEs as they are captured on the CRF pages for COVID-19 illness which are expected outcomes of the trial and are analyzed as efficacy endpoints.

In this trial, for subjects in the Immunogenicity/Reactogenicity Subset, information on solicited local and systemic AEs occurring within 7 days after each vaccination and on unsolicited AEs occurring within 28 days after each vaccination are collected.

For all trial subjects, information on medically attended AEs through 6 months after second vaccination and SAEs, AESIs and AEs leading to vaccine withdrawal or trial discontinuation through EOT are recorded.

Non-serious intercurrent medical conditions that may affect the immune response to vaccination are also collected as AEs throughout the trial.

No other AEs require recording in the CRF.

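### Protocol 9.3.3.2 and Appendix 10 tie eCRF recording of AEs to section 9.3.2 and omit 9.3.1, which contradicts the primary endpoint of 28-day unsolicited AEs in the subset

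*Protocol*

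**What the plan says.** Protocol 9.3.3.2 states that AEs volunteered by the subject (eDiary entries included) or found by the site "will be recorded in the eCRF if they fulfil the definitions as specified in section 9.3.2". Under AE Reporting in Appendix 10, the investigator documents AEs "which fulfil the conditions as outlined in section 9.3.2. Safety Assessments for All Subjects on the screens provided in the eCRF". A second sentence there again limits the Adverse Event screen to AEs that are reportable under 9.3.2. The amendment log for version 5.0 summarises the change as "AE recording only to be done for criteria defined in section 9.3.2".

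Section 9.3.2 has four classes. The first is "Medically-attended AEs will be collected through 6 months after the second trial vaccination"; the others are AESIs, SAEs, and AEs that lead to stopping vaccination or leaving the trial. It has no class for ordinary unsolicited AEs in the 28 days after a dose. Those are in 9.3.1, for the subset only, as "collection of unsolicited AEs on each vaccination day and the following 28 days".

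The primary safety endpoints in 4.2.1 include "Occurrence, intensity and relationship of unsolicited AEs occurring within 28 days after each trial vaccination in a subset of subjects". SAP 10.5 says that in the subset "unsolicited AEs occurring within 28 days after each vaccination are collected", and SAP 10.5.4 has the investigator transfer AEs from the eDiary to the CRF.

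**The concern.** Take a mild event on day 10 after a dose in a subset subject. It is self-treated, not serious, not an AESI, and does not stop vaccination. It counts toward the endpoint in 4.2.1, and SAP 10.5.4 puts it on the CRF. Under 9.3.3.2 and AE Reporting in Appendix 10 it meets no 9.3.2 class, so the stated condition for entry is not met. Two current documents therefore apply different reportability tests to the same event.

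This matters because the SAS 2 tables of unsolicited AEs (SAP 12.6.1.1, with an uncensored repeat of the 28-day overall summary in 12.6.1.4) count what is on the CRF. For unsolicited AEs, 9.3.1 describes the eDiary as a memory aid, so it is not a second dataset to fall back on. If some records were entered or cleaned under one test and some under the other, the table would mix two definitions.

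**Working it through.** **1. The passages side by side.**
- Recording tied to 9.3.2 only: Protocol 9.3.3.2 (one sentence) and Appendix 10, AE Reporting (two sentences).
- Recording of the subset's 28-day unsolicited AEs expected: 4.2.1 (endpoint); 9.3.1 (collection); the 9.1.1 visit procedures, which have staff review and record unsolicited AEs up to Day 57; 7.6, which puts therapies linked to these AEs in the eCRF; the AE and SAE Recording box in Appendix 10, which refers to Section 9.3 as a whole; SAP 10.5 and 10.5.4.

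The first group is narrower than the second by exactly the subset AEs that fall outside the four 9.3.2 classes.

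**2. The plan's own figure.** Protocol 10.1.1 says "solicited/unsolicited AEs with a true incidence of 5:1000 will likely be observed in this trial with a 98.5% probability of observing at least one", for 840 subset subjects on CVnCoV. P(at least one) = 1 − (1 − p)^n = 1 − (1 − 0.005)^840 = 98.5%, which reproduces. The upper bound after 0 events in 840 is 1 − 0.05^(1/840) = 3.56 per 1000, which matches the stated 3.6 as a one-sided 95% bound.

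**3. What the rule would do if it were followed throughout.** Let f be the share of 28-day unsolicited AEs that also meet a 9.3.2 class. The documents do not give f. I assume 0.10 to 0.75, the same for every AE type. Detection at 5:1000 becomes 1 − (1 − 0.005f)^840, and the bound becomes 3.56/f per 1000.
- f = 1 (both sections cited): 98.5%; 3.6 per 1000
- f = 0.75: 95.7%; 4.7 per 1000
- f = 0.50: 87.8%; 7.1 per 1000
- f = 0.25: 65.0%; 14.2 per 1000
- f = 0.10: 34.3%; 35.6 per 1000

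These values show how sensitive the plan's figure is to the rule. They do not estimate what happened.

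**4. Timing.** The log dates the restriction to 22 December 2021.
- A footnote in the SAP's opening section describes an early safety delivery for subjects randomized up to 11 February 2021. With dose 2 as late as the window allows, the last 28-day period for these subjects ends 28 + 7 + 28 = 63 days later, on 15 April 2021. That is 251 days before version 5.0.
- SAP 12.6.6 refers to a safety delivery on the first 1,037 subjects. If these are the same subjects (an assumption), 1,037/1,260 = 82% of the subset had closed windows by April 2021.
- For a window to be open on 22 December 2021, a dose would have been needed on or after 24 November 2021. That is four months after version 3.0 (23 July 2021) provided for unblinding every subject. The documents give no last-dose date, but an open window at that point is unlikely.

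**The case against.** The strongest reply is that nothing was lost. Almost all the data were collected before the wording existed, and the log calls it a clarification. The sentence in 9.3.3.2 says if, not only if. Much other current text shows that 28-day unsolicited AEs in the subset were meant to be on the CRF. SAP version 4.0 (8 April 2022) is later than protocol 5.0 and is to be read with it. Its section 10.5.8 treats an otherwise unclassified AE as over-reported only when it starts more than 28 days after a dose, so events inside that period stay in the tables.

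Most of this stands, and it limits the point. It does not remove it. SAP 10.5.8 acts only on records that are in the database; it cannot restore an event that was never entered or was closed as non-reportable. The other protocol text shows the intent, but the site's specific instruction on eCRF entry still points to the wrong list, in three places.

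Two stronger readings are tempting. A reader might infer that the rule removes most of the endpoint from the database. No passage reports or orders removal of existing records, and most would be lost only if f were below 0.5, which the documents do not show. A count of lost subjects would also need the proportion with any unsolicited AE, which is not given either. A reader might also extend the point to solicited AEs. Those have their own section (9.3.3.1) and their own CRF rule (SAP 10.5.2), and SAP 12.6.1.2 drops solicited analyses at end of trial.

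**Conclusion.** The contradiction is real and is in operative text: taken literally, the eCRF rule excludes events that a primary safety endpoint needs. It is a data-capture and consistency fault; no analysis method is wrong. Its effect on the reported rate cannot be derived from the documents, and the detection figures above apply only if the rule had governed entry throughout. That is not what the dates suggest. On the assumption that the two early safety deliveries cover the same subjects, at least about 82% of the subset was past its 28-day windows before the wording appeared, and probably all of it was. What remains is exposure of 28-day unsolicited AEs during late entry, querying and cleaning up to database lock. That is modest, but worth closing because the endpoint is primary and the correction costs almost nothing.

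**What to change.** In the one sentence of 9.3.3.2 and the two sentences of Appendix 10, AE Reporting, replace the reference to 9.3.2 with a reference to section 9.3.1 (Immunogenicity/Reactogenicity Subset) and section 9.3.2 (all subjects). Tell the site and the CRO in writing that subset AEs starting within 28 days of either dose are reportable and must not be removed or closed as non-reportable, in line with SAP 10.5 and 10.5.8. The eCRF audit trail (Protocol 11.1) can show whether any such record was changed after version 5.0.

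The cost is three cross-references, made as a protocol clarification or note to file, and one instruction. No new data, procedure or analysis is needed.

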### **9.3.3.3 Adverse Events of Special Interest**

AESIs will be collected through 1 year after the second trial vaccination. The following events will be considered as AESI during this trial:

- AEs with a suspected immune-mediated etiology (pIMDs, see Appendix 8).
- Other AEs relevant to SARS-CoV-2 vaccine development or the target disease (see Appendix 9).
- Non-serious intercurrent medical conditions that may affect the immune response to vaccination will also be collected throughout the trial.

### **9.3.4 Pregnancies**

Pregnancy is an exclusion criterion for enrollment in this trial, but subjects could potentially become pregnant during their active participation in this trial. Refer to Appendix 10 for details on the reporting and follow-up of pregnancies.

### **9.3.5 Safety Laboratory Assessments**

(See Appendix 5)

A urine sample for pregnancy testing will be taken from women of childbearing potential on Day 1 prior to trial vaccination to establish eligibility. A urine pregnancy test will also be performed before the second trial vaccination on Day 29 to continue to determine eligibility.

### **9.3.6 Vital Signs and Physical Examination**

At all trial visits (see Table 1 and Table 2), **vital signs** (body temperature, systolic/diastolic blood pressure and pulse) will be recorded in a standardized manner after the subject has rested in the sitting position for 5 minutes.

At the first trial visit on Day 1 and at the end of trial visit for all subjects in Trial CV-NCOV-005 (see Table 1 and Table 2), a complete **physical examination** will be performed, including examination of general appearance, eyes/ears/nose/throat, head/neck/thyroid, lymph node areas, cardiovascular system, lung/chest and abdomen, extremities and neurological examination, skin examination, measurement of weight and height. At all other trial visits, a symptom-directed physical examination will be performed at the discretion of the investigator and should include measurement of O2 saturation.

